**Parents and adolescent dyads display co-activation in the anterior insula.**

**APPROACH:** This study will utilize a rigorous multi-method, multi-informant design to examine the effects of dnf on adolescent brain activation with fMRI hyperscanning (see **Table 1** for Project Timeline). Parents and adolescents will also report on emotion regulation, depressive symptoms, and parenting practices. Data collection procedures will take place at the Laureate Institute for Brain Research (LIBR), which is equipped with two identical scanners

that have advanced real-time fMRI systems capable of conducting parallel fMRI hyperscanning, including the capacity for neurofeedback developed by [name], who is also [name] mentor. IRB approval will be obtained from the

Task	Year 1			Year 2		
	3/15/2019 - 8/15/2019	8/16/2019 - 12/15/2019	12/16/2019- 4/14/2020	4/15/2020 - 8/15/2020	8/16/2020 - 12/15/2020	12/16/2020- 3/14/2021
General Project Activities						
Weekly meetings with mentors	x	x	x	x	x	x
Protocol development and testing	x					
Train and hire RA	x					
Recruitment and Data Collection						
Recruitment and screening	5 dyads		5 dyads			
Scan sessions	5 dyads			5 dyads		
Data Entry, Analysis, and Coding						
Data entry and cleaning	x			x		
fMRI data processing and QA	x	x		x		
Transcription and coding of tasks	x	x		x	x	
Hypothesis testing		x				
Conference presentation			x	x		
Manuscript preparation					x	x
Preparation for K99/R00 Application						
Preliminary data analysis	x					
Draft research plan/revisions		x				
Finalize proposal and submit		x				

Oklahoma State University Center for Health Sciences.

Parents will complete a phone screen to determine initial eligibility (see Inclusion/Exclusion criteria in **Table 2**). If initial study criteria are met, a 2-hour in-person lab visit will be scheduled where mothers and daughters will complete consent/assent; diagnostic interviews (the Mini-International Neuropsychiatric Interview [parent MINI 7.0, adolescent MINI KID 7.0]); surveys on emotion regulation, parenting practices, depression, and anxiety (Table 3); and additional screening. Survey data will be used for preliminary exploratory analyses. Based on data collected from the screening visit, participants will be invited to participate in the full study: a 4-hour visit where mothers and daughters will complete emotion ratings, mock scanner training, and fMRI tasks individually and together using hyperscanning (scan time = 16 min resting-state [2 runs], 7 min structural MRI, 40 min fMRI tasks, 10 min clinical MRI scans).

**Participants.** 10 adolescents (ages 13-17; all female) and their biological mothers, total  $N=20$ , recruited using electronic flyers distributed through local schools and from a previous lab project (Dyadic Inter-Brain Signaling study). Our sample will include ~40% from ethnic/racial minority groups.

**Consideration of biological variables.** This study will result in pilot data and a protocol for a future intervention study in depression. Scientific reasons to only include females are: (1) rates of depression are three times higher among females than males; (2) during adolescence, female and male brains develop at

**Table 2: Inclusion/Exclusion Criteria**

Criteria	Moms	Girls
Inclusion		
Eligible for fMRI	✓	✓
Sufficient English fluency to complete tasks	✓	✓
BMI	18.0-40.0	16.0-40.0
Right-handed	✓	✓
Biological female	✓	✓
Biological mother	✓	
Co-residing at least 4 days/week	✓	✓
Primary caregiver > 50% of child's lifespan	✓	
Age 13-17		✓
Exclusion		
Current psychiatric diagnosis	x	x
Medications influencing fMRI	x	x
Medical conditions influencing fMRI	x	x
Alcohol or psychoactive drug on scan day	x	x
Neurodevelopmental delay		x
History of mood or psychotic disorder		x
History of OCD or ADHD		x

different rates, with some studies indicating a gap in brain maturation due to the onset of puberty occurring two years earlier for girls; (3) many adolescents do not have a consistent father figure in the home, with rates of 1 in 4 children living in single mother families; and (4) mothers and fathers diverge in emotion socialization techniques and parenting styles that could impact results.

**fMRI hyperscanning.** All hyperscanning experiments will be conducted on two MR750 3T MRI scanners with fMRI imaging protocols and parameters described elsewhere. Prior to scanning, participants will complete a brief training session in the mock scanner to desensitize them to the MRI environment and to practice talking while remaining as still as possible. After this training, subjects will complete an 8-minute eyes-open resting-state scan followed by the dnf training and transfer runs. Subjects will then undergo a second resting-state scan and complete post-scan emotion rating scales.

**Emotion Discussion with Dyadic Neurofeedback Task.** This task will be completed in the scanner using simultaneous hyperscanning data collection. Prior to the fMRI, adolescents (without the parent present) will be asked to think of recent situations when they were feeling strong negative emotions, such as anger, sadness, and/or anxiety. They will be informed that they will be talking to their mother about each situation during the scan. The mother (without the daughter present) will be provided with task instructions and informed that while talking to her daughter she will be receiving neurofeedback from a region in her daughter's brain. The mother will be told that her goal is to decrease activation in that region by calming her daughter and decreasing the intensity of her daughter's emotional response. The emotion discussion task will consist of four types of trials, each lasting 40s: Rest trials, Count trials, Discussion trials, and Reflection trials. During the first Discussion trial, the adolescent will describe the emotional situation. This will be followed by a second Discussion trial during which the mother will respond to the adolescent while receiving neurofeedback from the adolescent's aIC. This will be followed by a Count trial during which participants will mentally count backward from 300 by a number specified on the screen (for example, by 6: 300, 294, 288...) in order to bring aIC activation back to baseline. This will be followed by a 40s Rest period. Following the Rest trial, the adolescent will be provided 40s to respond to her mother (no neurofeedback presented), and the mother will subsequently respond again to the adolescent while receiving neurofeedback from her daughter's aIC. This will again be followed by a Count and Rest trial. Finally, both the adolescent and her mother will be asked to mentally (i.e., silently) reflect on the discussion while receiving neurofeedback representing the synchrony between both participants' aIC activation. This will be followed by another 40s Count trial and 40s Rest trial, for a total runtime of 8 minutes. Participants will complete three runs of the emotion discussion task with dnf, followed by a fourth transfer run in order to determine if the effects of the training persist. During the transfer run, the task will be exactly the same except no neurofeedback will be presented.

**Audio Collection and Coding.** Although collection of valid fMRI data during free speech requires extra care, we can correct for speech-related signal artifacts. In addition to standard pre-processing including volume registration and inclusion of motion parameters as covariates in regression analyses, we will use a continuous-speech 'de-noising' procedure developed by Xu et al. that employs a dual-mask spatial independent component analysis (ICA) method to identify noise components based on spatial origins. We will use active noise-cancelling microphones and headphones (OptoActive II NC Microphones and ANC Headphones, Opto acoustics Ltd.) and an intercom link between the scanners that produces voice/audio quality equivalent to most mobile phone calls. To avoid motion artifact interfering with the neurofeedback signal, neurofeedback will not occur when the subject of the neurofeedback is talking. The audio during the emotion discussion task will be recorded and later transcribed. The parents' responses will be coded for specific types of statements using the parent-child validation/invalidation behavior coding scales. Validating statements are supportive of the adolescent's emotional experience and show empathic understanding, while invalidating statements minimize, dismiss, or criticize the adolescent and/or her expressed emotions. In the proposed study, all transcriptions will be double-checked, and at least 2 of the 5 conversations will be double-coded. PI [name] will oversee coding, transcription, and reliability checks (80% agreement or higher).

**fMRI Data Acquisition Parameters.** fMRI data will be collected on two GE MR750 3 Tesla MRI scanners (scan time = 1hr 30m). Functional images will be acquired as echoplanar imaging (EPI, optimized to minimize signal dropout and image distortions; 46 contiguous 2.9-mm thick slices collected in the axial plane, ensuring whole-brain coverage [TR/TE = 2000/30 ms, SENSE acceleration R=2, flip angle = 90°, voxel size = 2.5×2.5×2.9 mm^3]). Both LIBR scanners are equipped with advance real-time fMRI systems, allowing for EPI

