**ANALYSES:** Data will be analyzed in real-time with LIBR software. An automated script will generate an anatomically-defined spherical region-of-interest (5mm radius) centered at the aIC (locus: [38, 16, 4], MNI space). The dnf, updated every 2s and shown as a bar with moving height, will be measured as % signal change relative to baseline (obtained by averaging the fMRI signal for the preceding 40s rest block). To reduce bar fluctuations due to noise in the fMRI signal, bar height will be computed at every time point as the mean of the current and two preceding fMRI signal change values. All offline fMRI data preprocessing and analyses will be conducted as described elsewhere. General Linear Models (GLM) will be used to analyze individual subjects' data with predictors in the model. Regressors of non-interest will be included in all models to account for each run's signal mean, linear, quadratic, and cubic signal trends, as well as motion parameters. Regressors will also include the block stimulus conditions (daughter: Describe/Respond, Listen, Count, Rest, Reflect; mother: Respond [dnf], Listen, Count, Rest, Reflect) and five polynomial terms for modeling the baseline. The GLM  $\beta$  coefficients will be computed for each voxel and converted to % signal change for contrasts of interest (e.g., Listen versus Count, Listen versus Rest, Count versus Rest, Reflect versus Rest, and Reflect versus Count). Statistical contrast maps for exploratory whole-brain analyses will include corrections for multiple comparisons.

**Hypothesis 1A.** *Mothers will perceive that they are able to influence their daughters' aIC activation using the daughter's fMRI neurofeedback signal (e.g., dnf), based on rating scales presented at the end of each run (i.e., average rating of ability to move bar  $\geq 5/10$ ).* We will ask the mother to rate how effective she felt she was at changing her daughter's brain activity on a Likert scale from 0-10. For this analysis, we will simply take the mean of all parent participants' responses over all runs and determine if it is at least 5, providing evidence that mothers perceived they were able to effectively regulate their daughter's brain activity.

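### Does the 8-minute task run need correcting, when the blocks listed add up to 440 s and no Rest is named before the first feedback block?

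*Combined protocol and SAP*

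**What the plan says.** The task paragraph in APPROACH gives one duration for all trials: "The emotion discussion task will consist of four types of trials, each lasting 40s". It then goes through the run in order. The daughter speaks first among the Discussion trials: "During the first Discussion trial, the adolescent will describe the emotional situation". Next comes a "second Discussion trial during which the mother will respond to the adolescent while receiving neurofeedback". A Count trial follows, and then the first Rest to be named: "This will be followed by a 40s Rest period". The daughter and mother each speak once more, followed by Count and Rest. Reflection with synchrony feedback comes next, and the paragraph closes with "This will be followed by another 40s Count trial and 40s Rest trial, for a total runtime of 8 minutes".

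The ANALYSES section expresses the feedback bar as a percentage signal change from a baseline "obtained by averaging the fMRI signal for the preceding 40s rest block". Under Hypothesis 1A, mothers report how well they could move the bar, "based on rating scales presented at the end of each run". Three runs carry feedback. The fourth, the transfer run, has none.

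**The concern.** Taken literally, the paragraph conflicts with itself and with ANALYSES. The named trials do not fill the stated run. If the run began with the daughter's description, the mother's first feedback block would come before any Rest in that run, so its bar would have no in-run baseline. In the first run there would be no earlier task Rest at all. That would affect one of the two mother-response blocks in each of the three feedback runs, or 3 of 6.

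This deserves a check because the study's stated product is a protocol for later, larger studies, and this paragraph is its core task specification. The bar is also what the mother is asked to act on, and her rating of her own effectiveness is the 1A measure. An undefined baseline could therefore affect what she sees and reports.

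**Working it through.** **Inputs.** Trial length is 40 s, stated run length is 8 minutes, and the order of trials is as described (all from the task paragraph). The bar baseline is the preceding 40 s Rest (ANALYSES). TR is 2 s (fMRI Data Acquisition Parameters). The allowance for fMRI tasks is 40 min (APPROACH, visit description).

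**Count as listed.** 4 Discussion + 3 Count + 3 Rest + 1 Reflection = 11 trials.

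- Listed time: 11 × 40 = 440 s = 7 min 20 s.
- Stated time: 8 × 60 = 480 s, and 480 / 40 = 12 blocks.
- Gap: 480 − 440 = 40 s, one block (40 / 480 = 8.3%; 220 against 240 volumes at TR 2 s).

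The stated 8 minutes is not reproduced from the list. Rounding does not explain it, since 7.33 min rounds to 7.

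**Position of Rest before each feedback block.** The middle column assumes that the listed trials start at 0 s. The last column adds one 40 s Rest at the start.

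| Feedback block | As listed | With an opening Rest |
|---|---|---|
| Mother, first response | 40–80 s; no earlier Rest | 80–120 s; Rest ended at 40 s |
| Mother, second response | 200–240 s; Rest ended at 160 s | 240–280 s; Rest ended at 200 s |
| Reflection | 320–360 s; Rest ended at 320 s | 360–400 s; Rest ended at 360 s |
| End of run | 440 s | 480 s |

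With the opening Rest, both mother-response blocks start 40 s after a Rest ends (80 − 40 and 240 − 200). The run becomes regular: Rest, daughter, mother, Count, twice; then Rest, Reflection, Count; then a closing Rest. That is 4 + 4 + 3 + 1 = 12 blocks.

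**Other uses of the 40 s.** End-of-run ratings might take some of it, but they supply no baseline. A previous run's closing Rest could not serve the first run. The resting-state scan before the task lasts 8 minutes, so it is not a 40 s block. Of the readings considered, only an opening Rest meets both the run length and the baseline rule.

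**Visit time.** Four runs take 4 × 480 = 1,920 s = 32 min, or 4 × 440 = 1,760 s = 29 min 20 s. Both fit within 40 min, so this figure does not decide between them.

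**What the analyses use.** Hypotheses 1B and 2B take offline timecourses from Reflection, which has a Rest directly before it either way. 2A uses offline coefficients from Listen trials, 3A uses the resting-state scans, and 3B uses ratings before and after scanning. None is computed from the bar. 1A averages the mothers' ratings, which the bar can influence only through what they see.

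**The case for a change.** The strongest case for a correction is that the written sequence is incomplete on any reading, and that even the favourable explanation concedes a missing block. A later team working only from this paragraph should not have to infer where a baseline comes from. The repair would be a line or two of text with no added scan time.

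The count behind this stands: 11 trials are named, 12 fit the stated run, and no readable passage names an opening Rest. The claimed harm does not follow. The text refers to the first trial of the Discussion type and does not say that this trial starts the run. Onsets that put the daughter's description at 0 s are therefore an assumption. To build a 440 s run with no first baseline, someone would have to disregard both the stated runtime and the baseline rule.

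Two sources that might show the sequence were also unavailable: a figure, and the cited real-time methods. Content that could be there cannot be called missing from the plan. Finally, the offline models' adjustment for each run's "signal mean, linear, quadratic, and cubic signal trends" has no bearing on the real-time bar, so it adds nothing to the concern.

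**Conclusion.** No change to the plan is needed. The discrepancy is real and small: one 40 s block out of 12 goes unnamed, and with it the Rest that would serve the mother's first feedback block. It is an incomplete listing that the stated run length and baseline rule together let a task builder complete. It is not an instruction that produces a wrong result.

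The conclusion rests on two things. First, an opening Rest is what was intended. This is inferred from the exact 480 s fit and the regular block pattern, and is not stated in the readable text. Second, no endpoint is calculated from the feedback bar, which the hypothesis descriptions in ANALYSES support. The sample size (10 dyads), every test and all offline analyses are the same under either reading. Any effect on the 1A mean would be indirect, and the documents allow neither a size nor a direction for it.

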**Table 3: Survey Measures**

Parenting
Child Report of Parent Behavior Inventory
Alabama Parenting Questionnaire
Emotion Socialization and Regulation
Emotion as a Child Scales
Difficulties in Emotion Regulation Scale
Mental Health – Adolescent
Mood and Feelings Questionnaire
Screen for Child Anxiety Related Disorders
Depression, Anxiety, and Stress Scale-21
Achenbach's Child Behavior Checklist (parent report)
Mental Health – Parent
Quick Inventory of Depressive Symptomatology – Self Report
Beck Anxiety Inventory
Depression, Anxiety, and Stress Scale-21

image quality examination and artifact troubleshooting before the subject begins the task scans, as well motion tracking during the scans. T1-weighted MRI anatomical MPRAGE high resolution (voxel size =  $1 \times 1 \times 1$  mm $^3$ ) images will be acquired. All imaging parameters, synchronization, audio, and visual coupling among the scanners have been, and will be, determined in consultation with LIBR's physicist, [name], who has developed and has experience with fMRI hyperscanning and will also serve as a mentor on the project.

**ANALYSES:** Data will be analyzed in real-time with LIBR software. An automated script will generate an anatomically-defined spherical region-of-interest (5mm radius) centered at the aIC (locus: [38, 16, 4], MNI space). The dnf, updated every 2s and shown as a bar with moving height, will be measured as % signal change relative to baseline (obtained by averaging the fMRI signal for the preceding 40s rest block). To reduce bar fluctuations due to noise in the fMRI signal, bar height will be computed at every time point as the mean of the current and two preceding fMRI signal change values. All offline fMRI data preprocessing and analyses will be conducted as described elsewhere. General Linear Models (GLM) will be used to analyze individual subjects' data with predictors in the model. Regressors of non-interest will be included in all models to account for each run's signal mean, linear, quadratic, and cubic signal trends, as well as motion parameters. Regressors will also include the block stimulus conditions (daughter: Describe/Respond, Listen, Count, Rest, Reflect; mother: Respond [dnf], Listen, Count, Rest, Reflect) and five polynomial terms for modeling the baseline. The GLM  $\beta$  coefficients will be computed for each voxel and converted to % signal change for contrasts of interest (e.g., Listen versus Count, Listen versus Rest, Count versus Rest, Reflect versus Rest, and Reflect versus Count). Statistical contrast maps for exploratory whole-brain analyses will include corrections for multiple comparisons.

**Hypothesis 1A.** *Mothers will perceive that they are able to influence their daughters' aIC activation using the daughter's fMRI neurofeedback signal (e.g., dnf), based on rating scales presented at the end of each run (i.e., average rating of ability to move bar  $\geq 5/10$ ).* We will ask the mother to rate how effective she felt she was at changing her daughter's brain activity on a Likert scale from 0-10. For this analysis, we will simply take the mean of all parent participants' responses over all runs and determine if it is at least 5, providing evidence that mothers perceived they were able to effectively regulate their daughter's brain activity.

**Hypothesis 1B.** *Mothers and daughters will be able to establish and maintain temporal synchronous aIC activation while reflecting on their interaction.* Correlations will be calculated between mothers' and daughters' aIC timecourses (Reflect vs Rest contrast).

**Hypothesis 2A.** *Mothers' own aIC activation while listening to their daughters will be positively correlated with that of their daughters' during the mothers' response.* The correlation between the mothers' and daughters' average beta weights for aIC activation during each participant's Listen trials will be calculated.

**Hypothesis 2B.** *Stronger temporal synchrony and coupling between mothers' and daughters' aIC activation during the reflection condition will be associated with more coded validation statements during the task and lower self-report ratings of negative emotions in both participants.* a) Coupling will be measured as the correlation between timecourses for aIC activation as described in Hypothesis 1B, transformed to z-scores (Fisher's r-to-z transformation). b) Participants will be asked to rate the intensity of various emotions they felt during the scan (0-10 Likert scale). Correlations will be calculated between the z-scores (a) and 1) the number of validating statements made by the mother across the scan and 2) ratings of negative emotions (b).

**Hypothesis 3A (Exploratory).** *Mothers' and daughters' neural activation of resting-state networks will be more temporally synchronous at the end of the hyperscanning session (following neurofeedback), as compared to their first resting-state fMRI scans in the hyperscanning session.* Similarity of resting-state networks will be evaluated as described in Lee et al. (2017). ICA will identify intrinsic resting-state networks at the group level. On the individual level, a matrix of correlation coefficients for all possible pairs of resting-state networks will be created and transformed to Fisher's z, then vectorized and correlated between each pair of mother-daughter dyads to determine the level of synchrony within the dyad. A paired t-test will be conducted to determine if there is a significant difference between resting-state synchrony at the beginning versus end of the scanning session.

**Hypothesis 3B.** *Ratings of positive emotions will be higher following the hyperscanning session as compared to ratings taken before the scan.* Paired t-tests will be conducted separately for mothers and daughters to determine if ratings of positive emotions (e.g., "happy," "calm") made on a 0-10 Likert scale before the scan differ significantly from those made after the scan.

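### Two separate gaps: read literally, the Hypothesis 1A mean includes the no-feedback transfer run; and no numbered hypothesis estimates daughters' aIC activation while mothers receive feedback

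*Combined protocol and SAP*

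**What the plan says.** **Runs.** The section on the Emotion Discussion with Dyadic Neurofeedback Task specifies three runs with feedback, "followed by a fourth transfer run in order to determine if the effects of the training persist". It adds: "During the transfer run, the task will be exactly the same except no neurofeedback will be presented".

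**Hypothesis 1A (ANALYSES).** The hypothesis is that mothers perceive they can influence their daughters' aIC through the feedback signal, "based on rating scales presented at the end of each run (i.e., average rating of ability to move bar", with a cut-off of 5 out of 10. The analysis text describes the item differently: the mother is asked to "rate how effective she felt she was at changing her daughter's brain activity", from 0 to 10. The decision rule is: "we will simply take the mean of all parent participants' responses over all runs and determine if it is at least 5".

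**Training goal.** Specific Aims gives the objective of training mothers to regulate their daughters' activation. The task section says the mother will be told that "her goal is to decrease activation in that region by calming her daughter". Aim 2 sets out to look at preliminary effects of the feedback on neural activation.

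**Activation model (ANALYSES).** The block conditions are "daughter: Describe/Respond, Listen, Count, Rest, Reflect; mother: Respond [dnf], Listen, Count, Rest, Reflect". The daughter's Listen blocks are those in which her mother responds. Signal change is computed for "contrasts of interest (e.g., Listen versus Count, Listen versus Rest" and others, given as examples. Offline methods are referred to cited sources.

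**The concern.** The two points do not depend on each other.

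1. In the transfer run there is no bar to move and no signal to use. A mother can still say how effective she felt at changing her daughter's brain activity, but that answer measures something other than the stated criterion. Because 1A is a bare threshold on a point estimate, a quarter of the ratings could decide the verdict for a reason unrelated to use of the feedback.

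2. 1A concerns perception only. If no hypothesis estimates the daughter's activation during the mother's response, the study can report on all its hypotheses without saying whether the trained target moved in the intended direction. The documents say that the protocol and early data will support a career-award application and later, larger studies, so readers will want that estimate.

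**Working it through.** **Point 1: the run scope of 1A**

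Inputs: three feedback runs and one transfer run (task section); 10 mothers (Participants); 0-10 scale and cut-off 5 (Hypothesis 1A). The plan gives no expected rating, SD, alpha or power for 1A, so it has no figure of its own to reproduce. D is the mean rating over the feedback runs and T the mean over the transfer run.

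- Ratings under the literal rule: 10 x 4 = 40, of which 10 come from the transfer run; 10/40 = 25%.
- Literal mean = (3D + T)/4, which differs from D by (T - D)/4.
- Setting this equal to 5 gives the critical value T = 20 - 3D, that is, T - D = 4(5 - D). T must therefore differ from D, toward and past 5, by about four times D's own distance from 5.
- T cannot be below 0, so a pass can become a fail only if 20 - 3D > 0, that is, D < 6.67. T cannot exceed 10, so a fail can become a pass only if 20 - 3D is at most 10, that is, D of at least 3.33.

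| D | Verdict on feedback runs | Literal rule reverses it if |
|---|---|---|
| 4.0 | fail | T is at least 8.0 |
| 4.5 | fail | T is at least 6.5 |
| 4.8 | fail | T is at least 5.6 |
| 5.2 | pass | T is below 4.4 |
| 5.5 | pass | T is below 3.5 |
| 6.0 | pass | T is below 2.0 |

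Illustrations with assumed ratings: D = 5.5 and T = 3.0 give (16.5 + 3.0)/4 = 4.875, a fail; D = 4.5 and T = 7.0 give (13.5 + 7.0)/4 = 5.125, a pass.

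Precision of the 1A mean: the 95% CI half-width is t(0.975, 9) x SD/sqrt(10) = 0.715 x SD. For an assumed between-mother SD of 2.0, 2.5 or 3.0 this is 1.43, 1.79 or 2.15 points.

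**Point 2: what each numbered hypothesis estimates**

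| Hypothesis | Quantity |
|---|---|
| 1A | mothers' perceived effectiveness |
| 1B | mother-daughter timecourse correlation during Reflect |
| 2A | correlation of mothers' and daughters' Listen betas |
| 2B | association of Reflect synchrony with validating statements and negative emotion |
| 3A | resting-state synchrony, start versus end of session |
| 3B | emotion ratings, before versus after the scan |

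Only 2A uses the daughter's activation while her mother responds. A correlation is unchanged when a constant is added to one variable: r(x, y + c) = r(x, y). A simulated check with 10 pairs gave r = 0.0156 with the daughters' values unshifted, raised by 1 and lowered by 1. So 2A could be confirmed whether daughters' activation fell, rose or stayed level.

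Data available for a direct estimate: the task has two 40 s blocks per run in which the mother responds, and TR is 2 s.

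- Feedback runs: 3 x 2 = 6 blocks per daughter, 6 x 40 = 240 s, 240/2 = 120 volumes.
- Transfer run: 2 blocks, 80 s, 40 volumes. Any single feedback run has the same amount.
- If one Listen regressor spanned all four runs, 2 of 8 blocks (25%) would be without feedback. The plan does not say whether it does.
- The 95% CI half-width for a mean over 10 daughters is 0.715, or about 0.72, of the between-daughter SD.

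**The case against.** **On point 1.** The reference to moving a bar suggests that the feedback runs alone may have been meant, and the text does not say outright that the transfer run is rated. That stands: this is an ambiguity that one phrase resolves. A reader might also infer that the 1A verdict is likely to be wrong. The documents do not support that, because they give no ratings and a reversal needs a large gap between T and D unless D is already near 5. In both illustrations the mean moves by only 0.625 points (2.5/4), less than the CI half-width under any of the assumed SDs.

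**On point 2.** A reader might infer that the study does not measure the daughter's response at all. It does: Listen versus Rest and Listen versus Count are listed, converted to percent signal change, and group summaries might be described in the cited sources. The mother's condition label mentions feedback and so fits only the feedback runs, which may mean that the transfer run is modelled separately. These limits stand, and the point is confined to the numbered hypotheses. None of them supplies a direction, a group summary or a link to an aim for the daughter's activation.

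It would also be wrong to take Listen below Count as the predicted result. Count is there to return aIC activation to baseline, and the documents do not predict that Listen falls below it. Rest is the better reference, since the feedback bar is itself scaled to the preceding Rest block. Regulation might also show as a fall across runs while activation stays above Rest.

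Finally, 1A already says that it concerns perception, and Aim 1 is labelled feasibility. That is correct, but Aim 2 goes further and names neural activation.

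**Conclusion.** Both points hold, separately. Aim 1 rests on perceived control and on synchrony during reflection whichever runs enter 1A, so the second point is not a consequence of the first.

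1. As written, the 1A mean gives 25% weight to a run without feedback. Its effect on the verdict is conditional: none if D is below 3.33 or at least 6.67, and otherwise only if T crosses 20 - 3D. This assumes four runs, all of them rated.

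2. No hypothesis from 1A to 3B estimates the level of, or change in, daughters' aIC activation while mothers receive feedback, although decreasing it is the stated goal. The statement covers the numbered hypotheses only, because the cited offline methods are not part of the documents.

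Both should be fixed: the changes are small and let Aims 1 and 2 answer their own questions.

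**What to change.** **Hypothesis 1A.** State that it is computed on the three feedback runs, with one mean per mother, and report the group mean with a 95% CI beside the cut-off of 5. Report the transfer-run rating separately. Use one wording of the item throughout. The cost is a clarifying sentence.

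**Daughters' aIC activation.** Add a descriptive companion, each estimate with a 95% CI:

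- percent signal change in Listen versus Rest for each feedback run;
- its change across the feedback runs;
- the same contrast in the transfer run, shown separately.

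Listen versus Count may be reported without a predicted sign. State that, with one arm and no sham, a decrease cannot be attributed to feedback rather than to habituation or to a change of topic between runs.

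**Cost.** No new data. Separate Listen regressors by run may be needed, since the plan does not say that condition betas are estimated per run. The transfer estimate, like that of any single run, rests on two blocks per daughter. With 10 dyads the estimates are imprecise and should not become a pass/fail test.
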